### **8.3 Recording Adverse Events**

The following subsections detail what information must be documented for each adverse event occurring during the time period specified in Section 8.2 Safety Assessment and Follow-Up.

The only portion of this study considered to be investigational is the maskless immobilization device (MID). Therefore, the only adverse events that will be reported are those related to the use of the MID.

#### **8.3.1 Relationship to Study Intervention**

The relationship to study device (MID) or study participation must be assessed and documented for all adverse events. Evaluation of relatedness must consider etiologies such as natural history of the underlying disease, concurrent illness, concomitant therapy, study-related procedures, accidents, and other external factors.

The following guidelines are used to assess relationship of an event to study intervention:

1. Related (Possible, Probable, Definite)
  - a. The event is known to occur with the study intervention.
  - b. There is a temporal relationship between the intervention and event onset.
  - c. The event abates when the intervention is discontinued.
  - d. The event reappears upon a re-challenge with the intervention.
2. Not Related (Unlikely, Not Related)
  - a. There is no temporal relationship between the intervention and event onset.
  - b. An alternate etiology has been established.

#### **8.3.2 Expectedness**

The PI is responsible for determining whether an AE is expected or unexpected. An AE will be considered unexpected if the nature, severity, or frequency of the event is not consistent with the risk information previously described for the intervention. Risk information to assess expectedness can be obtained from preclinical studies, the investigator's brochure, published medical literature, the protocol, or the informed consent document.

#### **8.3.3 Severity of Event**

Adverse events will be graded for severity according to the Common Terminology Criteria for Adverse Events (CTCAE) version 4.0

---

## **8.4 Safety Reporting**

The only portion of this study considered to be investigational is the maskless immobilization device (MID). Therefore, the only adverse events that will be reported are those related to the use of the MID.

### **8.4.1 Unanticipated Problem Reporting to IRB**

All incidents or events that meet criteria for unanticipated problems (UAPs), as defined in Section 8.1.1 Unanticipated Problems, require the creation and completion of an unanticipated problem report form (OHR-20).

UAPs that pose risk to subjects or others, and that are not AEs, will be submitted to the IRB on an OHR-20 form via the eazUP system within 5 working days of the investigator becoming aware of the event.

UAPs that do not pose risk to subjects or others will be submitted to the IRB at the next continuing review.

### **8.4.1 Adverse Event Reporting to IRB**

Grade 1 AEs are not required to be reported to the IRB.

Grade 2 AEs will be reported to the IRB at the time of continuing review if, in the opinion of the investigator, they represent events that exceed expected frequency or in some other way are judged to be unexpected and possibly associated with increased risk.

Other adverse events will only be reported if deemed related to the IRB.

### **8.4.2 Serious Adverse Event Reporting to IRB**

SAEs will be reported to the IRB on OHR-10 forms via the electronic reporting system (eSAEY) according to the required time frames described below.

Grade 3-4 AEs that are unexpected and deemed to be at least possibly or definitely related to the study will be reported to the IRB within 2 working days of knowledge of the event.

Grade 3-4 AEs that are deemed unrelated to the study will not be reported.

Grade 5 AEs that are deemed unrelated to the study will not be reported.

### **8.4.3 Reporting of Pregnancy**

No patients receiving radiation therapy should be pregnant. Department policy requires negative pregnancy test prior to starting radiation therapy. No additional protocol effort needed.

## **8.5 Halting Rules**

---

Study will be halted in the event of one serious adverse event definitely or probably related to the MID.

## 9 Study Oversight

In addition to the PI's responsibility for oversight, study oversight will be under the direction of the SKCC's Data and Safety Monitoring Committee (DSMC). The DSMC operates in compliance with a Data and Safety Monitoring Plan (DSMP) that is approved by the Clinical Trials Oversight Committee (CTOC).

## 10 Clinical Site Monitoring and Auditing

Clinical site monitoring and auditing is conducted to ensure that the rights of human subjects are protected, that the study is implemented in accordance with the protocol and/or other operating procedures, and that the quality and integrity of study data and data collection methods are maintained. Monitoring and auditing for this study will be performed in accordance with the SKCC's Data and Safety Monitoring Plan (DSMP) developed by the SKCC Data and Safety Monitoring Committee (DSMC). The DSMP specifies the frequency of monitoring, monitoring procedures, the level of clinical site monitoring activities (e.g., the percentage of subject data to be reviewed), and the distribution of monitoring reports. Some monitoring activities may be performed remotely, while others will take place at the study site(s). Appropriate staff will conduct monitoring activities and provide reports of the findings and associated action items in accordance with the details described in the DSMP.

## 11 Statistical Considerations

### 11.1 Study Hypotheses

**Primary objective:** To establish that the new device is no worse than the old device in term of the setup accuracy and reproducibility. Accuracy will be measured by quantifying the difference in translational shifts from the daily setup to planning CT scan digitally reconstructed radiograph (DRR). The magnitude of shifts will be compared to the shifts required using the gold standard thermoplastic mask.

**Secondary objective:** To establish that the new device is no worse than the old device in term of increasing patients' comfort and reduce patients' anxiety. The measurable outcome will be a questionnaire that assesses the patient's pain, discomfort and level of anxiety when in the MID compared to when in the thermoplastic mask.

### 11.2 Analysis Plans

For the primary objective, the magnitude of the single vector that depicts the degree of setup discrepancy from CT simulation will be collected for each patient on each day the MID is applied (for both the thermoplastic mask and the MID). The 90% lower

confidence limit of the absolute discrepancy, as well as the 90% higher confidence limit of the standard error, will serve as a conservative estimate of the mean and standard deviation. Based on literature, the thermoplastic mask results in a need for translational shifts on average of 3.5mm with a standard deviation of 1.2mm. We propose to use a total of 24 patients in the pilot study aiming to establish that the new device is no worse than the old device with a non-inferiority margin of 0.5mm, assuming the new device requires a mean translational error adjustment of patients by 2.5mm with the standard deviation of 1.2mm at 91% power and a Type-I-Error rate of 5%.

For the secondary objective, we will collect the preference survey scores for the thermoplastic mask versus the MID (survey results) from the same patients participated in the primary objective. The preference scores will be compared using cumulative logistic regression model.

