The proposed MID is a device that will allow the investigator to immobilize the patient without the use of a mask that covers the patient's face. Previous researchers have attempted to use maskless immobilization but the setup precision has historically been questioned. The current technology that is under review for provisional patent status (patent pending) will ensure reproducible immobilization in a non-invasive manner. The intellectual property under review is a device that allows quantification of the immobilization force and vectors. The patient will be positioned on a standard radiation therapy head rest and immobilized with two straps. Strap length will be adjusted by ratchets. Force gauges will be used to quantify how much pressure is applied through the strap, which allows the safe application of the strap, quantification of how much

tension is required for immobilization and reproducibility in subsequent treatment setups. Due to the force gauge quantifying the strap tension the risk of excess tension/pressure on the patient is theoretically less than strap application without the force gauge. This combination of commercially available technologies is the first application of its kind. The strap materials are regular tie down straps constructed of polypropylene, nylon or polyester. They are commercially available and are not the subject of intellectual property. Force gauges are also commercially available and will not have contact with the patient..

In regard to cost, after the initial cost of purchase for the MID (approximately \$50), the MID setup may be significantly cheaper than current thermoplastic masks. Each MID will require only two straps of material per patient. The cost may be as low as \$5 / patient, in contrast to the current price tag of \$250 / patient. Force gauge cost can vary from \$20 to \$1000. However, they will be part of the radiation table setup and not need to be purchased more than once.

This research will potentially lead to an additional standard of care for immobilization in head and neck RT. It is significantly less costly than the current standard of care. It will be more tolerable to patients with fears of enclosed spaces or objects on their faces. If it is comparable to the thermoplastic mask in regard to setup reproducibility, it may even replace thermoplastic masks.

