## 1.2 Rationale for the Proposed Study

The combination of the force gauge and strap for patient immobilization is the subject of intellectual property and does not exist outside this protocol. We propose that this combination allows for a safer application and reproducible immobilization of the patient compared to straps without force gauge quantification of pressure applied. However, the purpose of this study is not to evaluate safety, as the risk to patient with strap immobilization is extremely low. No radiation therapy will be delivered to the patient with MID immobilization.

The MID will be applied to the patient at CT simulation and two points during the treatment schedule, and no treatment will be delivered while the MID is applied to the patient. This will be two arbitrary time points to assess the degree of setup error compared to the gold standard of the thermoplastic mask. The patient population will be those patients being treated for head and neck cancers or intracranial tumors that requires radiation therapy (RT). This population is selected as the treatment fields are simple, and the setup position can be accurately verified by CBCT.

**SPECIFIC AIM 1:** To assess setup accuracy and reproducibility of the novel MID. We hypothesize that the degree of error with the novel MID will be similar to that of a thermoplastic mask.

---

---

**SPECIFIC AIM 2:** To assess the patient comfort and quality of life using the MID. We hypothesize that patients will have decreased claustrophobia symptoms and/or anxiety when immobilized with the MID compared to the thermoplastic mask.

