### **1.3 Potential Risks and Benefits**

#### **1.3.1 Potential Risks**

Some patients may experience anxiety or claustrophobia but this would likely be to a lesser degree than the thermoplastic mask in which they receive daily radiation treatments. Some patients may experience mild discomfort with the strap application to their foreheads and chins.

CBCTs are used in a regular basis for set up verification and deliver small amounts of additional radiation.

Rationale for additional imaging: No patient will receive radiation treatment with the experimental MID. Patient setup reproducibility and accuracy will be assessed by CBCT. Each day a patient is treated with radiation treatment, they are positioned to replicate the patient setup on the day the CT for radiation treatment planning was obtained. To verify this setup, images such as CBCTs can be obtained and compared to the original CT simulation scan. Since CTs are three dimensional, translational setup errors in the X, Y and Z axis can be quantified.

We need to obtain two additional setup CBCTs on two different treatment days. The CBCT with the MID will allow us to compare the MID setup with the CT simulation scan. The CBCT with the thermoplastic mask will allow us to assess setup error of the gold standard compared to the CT simulation scan. We can then compare the error of the thermoplastic mask with the experimental MID. **Patient safety and treatment will not be compromised as no treatments will be delivered with the MID.**

Safety of additional imaging: CBCTs are obtained by kV imaging. Each CBCT is approximately 5 cGy. The 4 additional CBCTs will add approximately 20 cGy to the patients overall radiation exposure. Patients receiving RT for primary brain tumors will be treated with 300x this dose (6000 cGy). Patients receiving radiation for head and neck cancers may receive doses of 6000-7000 cGy. Patients receiving RT for secondary/metastatic intracranial malignancies will receive 150x this dose (3000 cGy). Thus this additional imaging poses little if any risk to the patient and can ensure more accurate treatment setup and radiation delivery.

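### The primary no-worse claim covers reproducibility, but average shift length, the only quantity with a margin, cannot measure consistency between setups

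*Combined protocol and SAP*

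**What the plan says.** Section 11.1 states the primary aim: "To establish that the new device is no worse than the old device in term of the setup accuracy and reproducibility". Sections 2.1.1 and 2.2.1 also name accuracy and reproducibility together. Sections 2.2.1 and 11.1 then give a measure for accuracy only, the translational shift back to the planning scan, and say that shift magnitudes will be compared with those of the mask.

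Section 11.2 says that "the magnitude of the single vector that depicts the degree of setup discrepancy from CT simulation will be collected for each patient", for both devices, on each day the MID is applied. It describes the study as "aiming to establish that the new device is no worse than the old device with a non-inferiority margin of 0.5mm", with a mask mean of 3.5 mm, a MID mean of 2.5 mm, an SD of 1.2 mm for each, 24 patients, 91% power and a 5% type I error. It names no formal test. Its only item on spread is "the 90% higher confidence limit of the standard error", which is to serve as a conservative SD estimate.

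Reproducibility is not defined, and the text uses the word in two senses:

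- **Return to the planned position.** Section 1.3.1 says "Patient setup reproducibility and accuracy will be assessed by CBCT" and describes comparison with the simulation scan. Section 1.2 has a single hypothesis, that "the degree of error with the novel MID will be similar to that of a thermoplastic mask".
- **Consistency between setups.** Section 1.1 credits the force gauge with "reproducibility in subsequent treatment setups".

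**The concern.** A setup can miss the planned position by the same amount and in the same direction every day, or by the same amount in a different direction each day. The first is a repeated offset and the second is scatter. The unsigned length of the shift discards direction, so it cannot tell them apart. A conclusion drawn from average length would nevertheless be worded, under Section 11.1, as covering reproducibility.

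That part of the claim carries weight in the protocol's own rationale. Section 1.1 says: "If it is comparable to the thermoplastic mask in regard to setup reproducibility, it may even replace thermoplastic masks". If between-day consistency is meant, the study would support that statement without having examined it.

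**Working it through.** **1. The plan's own figure.** Take two independent groups of 12, SD 1.2 mm and a one-sided 5% level. The distance from the assumed true difference to the margin is 0.5 + (3.5 - 2.5) = 1.5 mm. The standardised distance is 1.5 / (1.2 × sqrt(2/12)) = 3.06. The non-central t distribution gives 90.7% power, which matches the stated 91%. The powered criterion is therefore a comparison of mean length, with no separate reproducibility component. (Each of the 24 patients is in fact measured with both devices. That is a separate matter and does not affect this point.)

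**2. A two-day example.** Let a patient's MID shifts (X,Y,Z, in mm) be:

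| Case | Fraction A | Fraction B | Lengths | Between-day change |
|---|---|---|---|---|
| Repeated offset | (2.5,0,0) | (2.5,0,0) | 2.5 and 2.5 | 0 |
| Scatter | (2.5,0,0) | (-2.5,0,0) | 2.5 and 2.5 | 5 |

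The plan's variable is identical in both cases.

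**3. The spread of lengths does not help.** In a simulation with isotropic normal errors (an assumption) and a mean length of 2.5 mm, the error was moved from all repeated offset to all daily scatter. Mean length stayed at 2.5 mm and the SD of lengths at 1.05 mm. The mean between-day vector difference rose from 0 to 3.5 mm. An upper limit on the spread or standard error of lengths is therefore not a within-patient, between-day measure. Section 11.2 also neither compares it between devices nor sets a criterion for it.

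**4. Size at the planning inputs.** Let M be the mean squared length (mean² + SD²) and c the share of M common to both days. If M is the same on both days and there is no common A-to-B change, the root-mean-square (RMS) displacement between Fractions A and B is sqrt(2 × M × (1 - c)).

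- Mask: M = 3.5² + 1.2² = 13.69
- MID: M = 2.5² + 1.2² = 7.69
- MID/mask ratio = sqrt(7.69 × (1 - c_MID) / (13.69 × (1 - c_mask)))

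| MID share | Mask share 0% | 50% | 75% | 90% |
|---|---|---|---|---|
| 0% | 0.75 | 1.06 | 1.50 | 2.37 |
| 50% | 0.53 | 0.75 | 1.06 | 1.68 |
| 75% | 0.37 | 0.53 | 0.75 | 1.19 |
| 90% | 0.24 | 0.34 | 0.47 | 0.75 |

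Equal shares give sqrt(7.69/13.69) = sqrt(0.562) = 0.75, in the MID's favour. The break-even mask share is 1 - 0.562 × (1 - c_MID), which is 44%, 72%, 86% and 94% for MID shares of 0, 50, 75 and 90%. At these inputs the MID scatters more only above those values.

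**5. Away from the planning inputs.** Suppose the true MID mean is 3.7 mm with SD 1.2 mm, which is worse than the mask but inside the 0.5 mm margin. Then M = 3.7² + 1.2² = 15.13, and equal shares give sqrt(15.13/13.69) = 1.05. With equal means of 3.5 mm but a MID SD of 2.0 mm, M = 16.25 and the ratio is sqrt(16.25/13.69) = 1.09. In both cases the MID scatters more although the shares are equal.

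**The case against.** The strongest reply is that the protocol mostly uses reproducibility to mean return to the simulation position. On that reading distance from simulation does measure it, and scatter does lengthen the average shift. This stands in part. A reader might infer that reproducibility goes wholly unmeasured, and the documents do not support that. The gap is consistency between setups, the sense used in Section 1.1. No section says how one MID day is to be compared with the other.

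A reader might also infer that the MID is likely to scatter more than the mask. Nothing in the documents shows this. Neither share of repeated offset is given, and equal shares at the planning inputs favour the MID. Nor is it right that extra scatter could arise only if more of the mask's error is a repeated offset. That condition is necessary at the planning inputs, though not sufficient. It is not necessary when the MID's true lengths are larger but still within the margin (step 5).

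It can further be said that axis shifts will exist anyway. Section 1.3.1 says that errors on the three axes can be quantified, and Section 13 says that shifts are recorded. Neither says that signed components are kept for each device and fraction, and no analysis uses them.

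Finally, this is a small pilot, no treatment is given in the MID, and the remark about replacing masks is conditional background rather than a decision rule. That limits the stakes and argues for a short remedy. But the plan still sets a margin, power and error rate in order to establish a no-worse claim, and that claim should not reach beyond what is measured.

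**Conclusion.** The concern holds for between-day reproducibility. Meeting the 0.5 mm criterion on average length would support a no-worse conclusion on accuracy, and partly on return to the planned position. It would not support one on consistency between setups.

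The missing measure and criterion are clear from the text. The practical effect is not known. Over repeated shares of 0 to 90%, the between-day ratio at the planning inputs runs from 0.24 to 2.37, so the direction of any effect cannot be stated. These ratios assume the means and SDs in Section 11.2, equal mean squared length on both days and no common A-to-B change. The two-day example needs none of these assumptions. The plan should be changed, but the point does not put the accuracy comparison in doubt.

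**What to change.** Keep the vector magnitude and its 0.5 mm margin for accuracy. In addition:

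1. State that signed X, Y and Z shifts are recorded for each device at Fractions A and B.
2. Define reproducibility as between-day consistency. For each device and axis, report the mean A-to-B change and the within-patient SD, taken as the SD of A minus B divided by sqrt 2.
3. Report the MID/mask ratio of the combined three-dimensional within-patient SD (the root of the summed axis variances). Give it a confidence limit that keeps each patient's two devices together, for example from a leave-one-patient-out jackknife of the log ratio.
4. Compare the mean A-to-B change between devices as well. The within-patient SD removes any change common to all patients, so a uniform drift would not show in the ratio.
5. Unless a margin is justified in advance, treat items 2 to 4 as estimation and limit the formal no-worse conclusion in Section 11.1 to accuracy.

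The estimate would be usable at this size. In simulations with Gaussian shifts and 24 patients, the jackknife one-sided 95% upper limit covered 94.8% to 95.4%, and its median was 1.20 to 1.29 times the observed ratio. With an assumed 16 completers the median was 1.26 to 1.38 times.

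The cost is a few spreadsheet columns, a little more analysis and a narrower formal claim. The schedule in Section 6 already has a CBCT for both devices at both fractions, so no extra imaging, visits or patients are needed.

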### 2.2 Endpoints/Outcome Measures

#### 2.2.1 Primary

The primary endpoints are to assess the setup accuracy and reproducibility with the MID. Accuracy will be measured by quantifying the difference in translational shifts from the daily setup to planning CT scan digitally reconstructed radiograph (DRR). The magnitude of shifts will be compared to the shifts required using the gold standard thermoplastic mask.

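### Section 11.2 uses a limit of the standard error as the SD and a lower limit of setup error as a conservative mean, and ties neither to the 0.5 mm margin, so the stated 5% Type I error is not secured

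*Combined protocol and SAP*

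**What the plan says.** Section 11.1 sets the primary aim: "To establish that the new device is no worse than the old device in term of the setup accuracy and reproducibility". Section 2.2.1 adds only that "The magnitude of shifts will be compared to the shifts required using the gold standard thermoplastic mask".

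Section 11.2 defines the measurement: "the magnitude of the single vector that depicts the degree of setup discrepancy from CT simulation will be collected for each patient on each day" that the MID is applied, for both devices. It then gives its single estimation rule, which takes a lower limit at the 90% level for the mean and pairs it with a second limit for the spread: "confidence limit of the absolute discrepancy, as well as the 90% higher confidence limit of the standard error, will serve as a conservative estimate of" those two quantities.

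The margin and error rate come later, in the sizing sentence. The aim there is to show the MID "no worse than the old device with a non-inferiority margin of 0.5mm", assuming a MID mean of 2.5 mm against 3.5 mm for the mask and a "standard deviation of 1.2mm at 91% power and a Type-I-Error rate of 5"%. Section 11.3 only refers back to 11.2. No test, no interval for the difference between devices and no success criterion is given.

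**The concern.** There are three separate problems.

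- **Quantity.** A standard error measures the precision of a mean, not the spread of the data. An upper limit of the standard error is not a conservative SD; with 24 patients it is far below the SD.
- **Direction.** The discrepancy is the length of an error vector, recorded for each device, so larger is worse. For a no-worse claim, cautious handling of the MID needs an upper limit. A lower limit flatters whichever device it is applied to.
- **Link.** Nothing connects these limits to the 0.5 mm margin. The plan does not say whether 90% is one- or two-sided, which device or contrast the limits apply to, or that the comparison is paired.

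Two things are at stake. Reproducibility is half of the primary aim, and its spread would be reported as much too small. For accuracy, the analyst could choose among readings after seeing the data, and some of them do not hold 5%.

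**Working it through.** **Inputs from section 11.2:** 24 patients, both devices in each; SD 1.2 mm for each device; means 3.5 mm (mask) and 2.5 mm (MID); margin 0.5 mm; Type I error 5%; power 91%.

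**Assumptions, because the plan is silent:** normal data; one value per patient and device (n = 24); within-patient correlation between devices 0 or 0.5; 90% read either as one-sided or as one end of a two-sided interval.

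**1. The plan's own power.** The distance from the assumed difference to the margin is 0.5 − (2.5 − 3.5) = 1.5 mm. For two independent groups of 12, SE = 1.2 × √(2/12) = 0.490 mm and the noncentrality is 1.5/0.490 = 3.06. At one-sided 5% the power is 0.907 (noncentral t) or 0.922 (normal approximation). At one-sided 2.5% it is 0.833 or 0.865. So 91% reproduces as 12 against 12 at one-sided 5%. This shows the level intended, and that the sizing ignored the pairing.

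**2. Standard error taken as SD.** SE = 1.2/√24 = 0.245 mm. The upper-limit factor is √(23/χ²), with χ² the lower 10% or 5% quantile on 23 df: 1.245 (one-sided 90%) or 1.326 (two-sided 90%).

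- Limit of the SE: 0.245 × 1.245 = 0.305 mm, or 0.245 × 1.326 = 0.325 mm. That is 25% or 27% of 1.2 mm, hence 3.7 to 3.9 times too small.
- Limit of the SD: 1.2 × 1.245 = 1.49 mm, or 1.2 × 1.326 = 1.59 mm.

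**3. Lower limit taken as the mean.** With t(23) = 1.319 or 1.714, the mean is understated by 1.319 × 0.245 = 0.323 mm or 1.714 × 0.245 = 0.420 mm, which is 65% or 84% of the margin.

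**4. Type I error by reading.** The true difference is set at the margin (MID 4.0 mm, mask 3.5 mm), with 200,000 simulated trials. Columns give the correlation (ρ) and the reading of 90%.

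| Reading | ρ=0, one-sided | ρ=0, two-sided | ρ=0.5, one-sided | ρ=0.5, two-sided |
|---|---|---|---|---|
| Lower limit of mask minus MID above −0.5 mm | 10.1% | 5.0% | 10.0% | 5.0% |
| MID lower limit as its mean, then 5% paired t test | 22.6% | 31.5% | 35.1% | 49.7% |
| Same, with upper limit of the SD | 12.7% | 15.8% | 22.1% | 30.1% |
| Lower limit on both devices, then paired t test | 5.3% | 5.5% | 5.4% | 5.6% |
| Lower limit on the mask only | 0.7% | 0.3% | 0.2% | 0.1% |
| Observed means; SE limit entered as SD and divided by √24 again | 33.4% | 32.4% | 33.3% | 32.3% |
| Observed means; SE limit used as the SE | 2.2% | 1.6% | 2.2% | 1.6% |

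A hand check of the second row at ρ = 0.5, one-sided: the SE of the paired difference is 1.2 × √(2 × 0.5)/√24 = 0.245 mm. Subtracting 0.323 mm moves the t statistic by 0.323/0.245 = 1.32. The effective critical value falls from 1.714 to about 0.395, which gives a tail probability near 35%.

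**5. A paired rule on the same data.** The SD of the difference is 1.2 × √(2(1 − ρ)), or 1.70 mm at ρ = 0. The noncentrality is 1.5/(1.70/√24) = 4.33. Power at one-sided 5% is 0.9947 at ρ = 0, 0.9996 at 0.3 and above 0.9999 at 0.5. Simulated Type I error is 5.0%.

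**6. Why reproducibility needs its own SD.** Averaging two fractions hides day-to-day variation. With a single-fraction SD of 1.2 mm and an assumed between-patient variance share s of 0.2, 0.5 or 0.8, the SD of the two-fraction mean, 1.2√(s + (1 − s)/2), is 0.93, 1.04 or 1.14 mm. The between-fraction SD, 1.2√(1 − s), is 1.07, 0.85 or 0.54 mm.

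**The case against.** The best defence is that the sentence is not a decision rule. Limits that stand in for a mean and an SD read like cautious planning values for a later trial, and this is a pilot. If the discrepancy meant the gain of the MID over the mask, a lower limit of the gain and an upper limit of the spread would be the cautious pair, and standard error would be a slip for standard deviation. Likewise, a two-sided 90% interval fits a one-sided 5% test, and the lower limit of mask minus MID against −0.5 mm holds 5.0%. The 23 to 50% figures need the limit to be applied to the MID alone, which the plan does not say.

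Much of this is fair. If standard error is a slip, an upper limit is conservative and only the word needs correcting. No single error rate can be attributed to the plan. But 11.2 defines the discrepancy per device rather than as a difference, and it presents the rule as serving the primary objective. If planning values were meant, 11.2 contains no primary test at all, although it states a margin, a power and an error rate.

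The unit of analysis also matters. Treating 48 patient-days as independent would put the SE limit at about 0.17 of the SD, which is worse; 12 per group would put it at 0.41 to 0.45. Using two-fraction means (SD 0.93 to 1.14 mm), the understatement of the mean is 1.319 × 0.93/√24 = 0.25 mm to 1.714 × 1.14/√24 = 0.40 mm, or 50 to 80% of the margin. The conclusion does not change.

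Finally, participants are not at risk, since no radiation is delivered with the MID, and the individual vectors are kept, so a correct analysis remains possible.

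**Conclusion.** The concern holds. Taking a standard-error limit as the SD is wrong as written: with one value per patient, 24 patients and an SD of 1.2 mm, it gives 25 to 27% of the true spread. Calling a lower limit of a larger-is-worse measure conservative is wrong when it is applied to the MID or to MID minus mask; it is about neutral on both devices with equal SDs, strict on the mask alone, and right for a two-sided 90% interval of mask minus MID. Because the plan does not choose among these, the 5% is not secured. The Type I error rates rest on normal data and assumed correlations, and belong to assumed readings rather than to a stated rule. The damage is to the interpretation of the pilot and to planning from it. This should be fixed before the data are analysed.

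**What to change.** Replace the sentence on the 90% limits with:

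> For each patient, compute MID minus mask vector error, averaged over the available fractions (A and B). Non-inferiority in accuracy is declared if the upper limit of the two-sided 90% confidence interval (one-sided 5%) of the mean within-patient difference is below +0.5 mm. For reproducibility, report each device's SD, including the within-patient between-fraction SD, with its upper confidence limit.

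Then:

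- Say that the 0.5 mm criterion covers accuracy only. Either give reproducibility its own criterion or call it descriptive and adjust section 11.1 to match.
- Delete the use of a standard-error limit as the SD.
- Restate the power for the paired design.
- If the limits are meant as planning values for a later study, say so separately from the primary test.

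The cost is wording only, with the same patients and the same data. If up to 20% of patients have only one fraction (assumed at random, devices independent, same variance shares as in step 6), simulated Type I error stays at 5.0% and power is at least 99.6%.
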